# 4.2. Description of the research methodology, including a schematic diagram with details of planned visits and examinations

# 4.2.1. Experimental design

- Phase IV drug trial
- Regional multicenter study (La Roche sur Yon, Le Mans, Nantes)
- Comparative
- Randomized
- Controlled
- Control group: reference arm (Diprostene®) and 0.9% NaCl
- Of superiority
- Double-blind (patient and evaluator)
- In 2 parallel groups: one with injection of CTC and 0.9% NaCl; the second with injection of HA and CTC

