### 4.2.2. Course of the study

### 4.2.2.1. Inclusion

Inclusion and non-inclusion criteria will be verified in a pre-inclusion visit.

On this occasion, the study will be presented to the patient, together with oral and written information and the informed consent form.

During the inclusion visit, the informed consent form and data for the various parameters mentioned above will be collected by means of a clinical examination; an initial ultrasound scan in B mode and Doppler mode, a pain VAS (at rest and during activity), the Cochin scale, grip and opposition strength and a pain VAS during the infiltration procedure.

Two (2) doctors at each center will be investigators and will manage the iterative evaluations. One (1) to two (2) doctors per center will perform the infiltrations; these doctors will not be evaluating doctors.

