### 4.3. Description of measures taken to reduce and avoid bias

## 4.3.1. Drawing of lots

Randomization will be blinded to patient and evaluator, with 2 groups of patients: one group receiving an injection of hyaluronic acid combined with corticosteroids, and the other receiving an injection of corticosteroids and 0.9% NaCl. Randomization will be stratified by center. It will be carried out in a 1:1 ratio and in blocks.

Capture System software will be used for randomization by connecting to the website: https://www.dirc-hugo-online.org/csonline/. A login, password and study number will be issued by a data manager in the Research Promotion Department of La Roche sur Yon Hospital. The following information must be provided:

- First initial of the last name,
- First initial of the first name,
- Month and year of birth,
- Compliance with inclusion and non-inclusion criteria (yes/no),
- Signing of the informed consent (yes/no).

Randomization will be carried out by the investigator once the possibility of inclusion in the study has been confirmed and the patient's informed consent has been signed.

The inclusion number will be assigned automatically during randomization. A confirmation e-mail will be sent to the person who carried out the randomization, as well as to all those concerned.

The randomization list will be drawn up by a statistician from the Research Promotion Department of La Roche sur Yon Hospital. An explanatory guide to randomization will be available online in Capture System.

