# Primary endpoint:

The VAS on activity at 3 months will be compared between groups using a mixed model, taking account of the initial VAS as a fixed effect and the center as a random effect.

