# Secondary endpoints:

- Changes in pain at rest and during activity over time will be compared between groups, using random-effects models to account for inter-individual variability modeled via random effects (based on the idea that patients represent a random sample from a larger population), as well as intra-individual variability modeled via measurement error; the group effect (HA + CTC vs. CTC alone), time (M0, M1, M3, M6, M12) and their possible interaction will be estimated and tested.
- Changes in **Cochin scale** parameters, **grip strength** and **opposition strength over** time will be compared between groups using random-effects models. The effect of group (HA + CTC vs. CTC alone), time (M0, M1, M3, M6, M12) and their possible interaction will be estimated and tested.
- The proportion of patients with a change in **ultrasound score** between D0 and M3 will be compared between groups using a Chi2 test.
- The VAS of pain at the time of injection will be compared between the two groups using a Student's t test.
- The number of **new infiltrations** during the follow-up year will be compared between groups using a Student's t test.
- Adverse events will be described for each group in terms of numbers and percentages.
- Changes in **analgesic use** will be compared between groups using random-effects models. The group effect (HA + CTC vs. CTC alone), time (M0, M1, M3, M6, M12) and their possible interaction will be estimated and tested.
- The number of days **off work** during the follow-up year will be compared between groups using a Student's t test.
- The rate of patients undergoing **surgery** will be compared between groups using a Chi2 test.

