# 15. Study feasibility

The teams involved in this study include rheumatologists trained in osteoarticular ultrasound, with several years' experience in ultrasound-guided infiltration procedures. Some of these doctors are instructors for a DIU (inter-university diploma) for guided osteoarticular procedures. In terms of recruitment, the CHD Vendée recruits approximately 100 patients with rhizarthrosis requiring infiltration per year, 60 at the CHU Nantes and approximately 40 at the CHG Le Mans, i.e., 200 patients per year (and 300 in 18 months). Taking into consideration non-participants (refusals, non-inclusion criteria, etc.), the number of 150 patients to be included seems realistic.

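### Centre is a randomisation stratum and is in the primary model, but the five t and Chi2 tests on secondary outcomes ignore it, which costs some power if centre affects those outcomes

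*Combined protocol and SAP*

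**What the plan says.** Section 4.3.1 sets the design: "Randomization will be stratified by center", and "It will be carried out in a 1:1 ratio and in blocks". The block size is not given. Section 4.2.1 names three centres.

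For the primary endpoint, section 9.1 specifies a mixed model "taking account of the initial VAS as a fixed effect and the center as a random effect".

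For the secondary endpoints, section 9.1 does not mention centre:
- Injection pain: "The VAS of pain at the time of injection will be compared between the two groups using a Student's t test". The counts of new infiltrations and of days off work also get Student's t tests.
- Change in ultrasound score and the rate of surgery get Chi2 tests.
- Rest pain, activity pain, the Cochin scale, grip strength, opposition strength and analgesic use get random-effects models with group, time (M0 to M12) and their interaction. The item on pain describes its random effects as between-patient. The other items do not list theirs.

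Section 9.6, on changes to the analysis plan, is marked not applicable, and no other section adds centre to these analyses.

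**The concern.** Blocked allocation within centre balances the arms on centre. Any difference in level between centres therefore drops out of the true sampling variance of the treatment difference. A test that ignores centre still counts that variation as error. Its standard error is too large, its real type I error is below the nominal 5%, and it has less power than the data allow.

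Injection pain is where a centre effect is easiest to imagine: "One (1) to two (2) doctors per center will perform the infiltrations" (section 4.2.2.1), so operator and centre nearly coincide, and the planned test has no covariate.

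There is also a matter of consistency. The primary analysis follows the randomisation and these analyses do not. If centre were added after the data had been seen, it would be an unplanned choice.

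**Working it through.** **The plan's own figure.** The only computed figure is the primary sample size in section 9.2. The difference is 0.35 × 6.4 − 0.25 × 6.4 = 0.64, with SD 1.3. At two-sided 5% and 80% power the normal formula gives 2 × (1.96 + 0.84)² × (1.3/0.64)² ≈ 65 per arm (130). The t-based version gives 66 per arm, which is the stated 132. The figure reproduces but says nothing about the secondary tests, for which no power is stated.

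**Inputs.** There are 150 patients, 75 per arm (9.2). Section 15 gives about 100 patients a year at the sponsor's hospital, with "60 at the CHU Nantes and approximately 40 at the CHG Le Mans". Shares of 50%, 30% and 20% of 150 give 75, 45 and 30 patients. The share s of outcome variance that lies between centres is not documented, so it is an assumption, shown over a range.

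**t tests.** With 1:1 allocation inside centres:
- SE reported by the plain t test = SD × √(2/75)
- true SE = SD × √(1 − s) × √(2/75)
- ratio r = 1/√(1 − s)
- actual two-sided alpha = 2 × [1 − Φ(1.96 r)]
- power, for an effect that the centre-adjusted test detects with 80% power = Φ(0.84 + 1.96 × (1 − r))

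Example, s = 0.10: r = 1.054. Alpha = 2 × [1 − Φ(2.066)] = 3.9%. Power = Φ(0.736) = 76.9%.

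| Assumed centre share s | SE overstated by | Actual alpha | Power (adjusted test 80%) |
|---|---|---|---|
| 0 | 0 | 5.0% | 80.0% |
| 1% | 0.5% | 4.9% | 79.7% |
| 2% | 1.0% | 4.8% | 79.4% |
| 5% | 2.6% | 4.4% | 78.5% |
| 10% | 5.4% | 3.9% | 76.9% |
| 20% | 11.8% | 2.8% | 72.9% |

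**Simulation check.** This used 8,000 trials per setting, centres of 75/45/30, blocks of 4 within centre and SD 1.3. At s = 0.10 the plain t test reported a mean SE of 0.212 against an empirical SE of 0.200 to 0.203. It rejected 3.8% of true nulls; with centre in the model the figure was 4.9%. At a difference of 0.64 its power was about 87%, against 89% with centre. At s = 0 the two analyses agreed.

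**Chi2 tests.** The SE ratio is √[p(1 − p) / Σ w p_c(1 − p_c)], with weights w of 0.5, 0.3 and 0.2, centre rates p_c and overall rate p. All rates are assumed.
- 40/30/20%: √(0.2211/0.2150) = 1.014.
- 50/30/10%: √(0.2304/0.2060) = 1.058.
- An uncommon outcome, 8/5/2%: √(0.0555/0.0550) ≈ 1.005.

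**Longitudinal models.** M0 is one of the response times, so a treatment effect on change appears as the group-by-time interaction. That is a within-patient contrast, and a constant centre offset cancels from it. In the same simulation at s = 0.10, change scores rejected 5.25% of true nulls without centre and 5.24% with it, and the SEs were equal. In a small repeated-measures check (40 trials, centre share 13%, 10% of visits missing), the interaction SE was 0.2138 without centre and 0.2137 with it. The SE of the group main effect fell from 0.224 to 0.208. Only the group main effect is affected.

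**The case against.** Four arguments can be made for leaving the plan alone.

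**No centre effect is shown.** The documents give no centre variance, and they describe standardised injection at each site (4.2.2.2), standardised dynamometry and graded ultrasound scoring (4.1.2). This stands. Having few operators per centre makes a centre effect on injection pain plausible but does not demonstrate one. A reader might infer that strength, ultrasound grading or decisions to re-inject differ by local staff; no section says so.

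**Most comparisons escape.** A reader might infer that every secondary comparison loses power. That is not supported. Six of the eleven outcomes with a planned comparison use longitudinal models whose group-by-time test is essentially untouched. Nor does the plan exclude centre from all of those models: only the item on pain describes its random effects, and the others are silent.

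**The error is conservative and usually small.** This also stands. Type I error falls below 5%, so no excess of false positive findings follows, and the primary analysis is not involved. For centre shares up to 2%, the loss is under one power point.

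**The remedy is not entirely free of choices.** A centre-stratified test of surgery may meet sparse strata: at an assumed 5% rate, a centre of 30 expects 30 × 0.05 = 1.5 events. A linear model for new infiltrations or days off work is still a normal-theory analysis of counts. The first is met by an exact version. The second applies equally to the planned t tests and is a separate question.

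These arguments limit the scope and size of the point. They do not explain why five tests should ignore a factor by which the trial randomises.

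**Conclusion.** The point holds for the three t tests, the two Chi2 tests and the group main effect of the longitudinal models. If centre is related to the outcome, their standard errors are too large and the tests are conservative. For the t tests the loss is about 0.3 to 3 power points at assumed centre shares of 1% to 10%, and about 7 points at 20%. For the Chi2 tests the standard error is overstated by about 0.5% to 6% under the assumed centre rates. With no centre effect there is no loss.

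The size rests on undocumented centre shares and rates, on centre sizes taken from the feasibility section, and on near balance within centres. A reader might go further and conclude that the secondary results would be invalid or biased. The documents do not support that: the issue is efficiency and consistency with the design.

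**What to change.** In section 9.1, under the secondary endpoints:
1. Replace the three t tests (injection pain, new infiltrations, days off work) by linear models with arm and centre.
2. Replace the two Chi2 tests (ultrasound change, surgery) by Cochran-Mantel-Haenszel tests stratified by centre, with an exact version if surgery events are sparse.
3. Include centre in the longitudinal models for consistency with the primary model, and state whether it is fixed or random. Note that this helps the group main effect and not the group-by-time test.

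The cost is wording and, with centre as a fixed effect, two degrees of freedom: with 150 patients the residual goes from 148 to 146 in the linear models. Centre is already recorded at randomisation, so no new data are needed, and no endpoint or sample size changes. The change should be made before the data are unblinded.

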## 4.1.2. Secondary endpoints

- VAS recorded at inclusion, M1, M6 and M12 post-infiltration.
- Recording of VAS between 0 and 3 months.
- This will be done by means of weekly VAS measurements taken by the patient himself/herself, recorded in a notebook given to the patient.
- A VAS of perceived pain at the base of the thumb will be recorded at rest at inclusion, and at 1, 3, 6 and 12 months.
- The worst Pain Score at M0, M1, M3, M6 and M12.
- Cochin score at inclusion, M1, M3, M6 and M12.

This score incorporates the inability to cook, get dressed, wash, work and perform other activities reported by the patient. It ranges from 0 to 90: the higher the score, the greater the impact of the rheumatological pathology on hand function. This index has been validated for its reliability, validity, and sensitivity to change in the arthritic hand.  The questionnaire takes an average of 3 minutes to complete, has an inter-observer correlation of 0.96 and good construct validity. Another advantage of this scale is the capacity to discriminate between improving and deteriorating patients.

- Grip and opposition strength.

Measurements will be carried out using two different JAMAR dynamometers according to a standardized methodology;

The first allows measurement of opposition strength, expressed in kilograms. The thumb-index grip of the dominant and non-dominant hands is measured 3 times. A one-minute rest period is observed between each test. The highest values will be used.

The second measures grip strength in kilograms.

These two strengths will be assessed at inclusion, and at 1, 3, 6 and 12 months.

- Ultrasound evaluation at inclusion and M3.

Initial ultrasound data will be collected at M0 in B and Doppler modes, and at 3 months. The appearance of lesions on ultrasound will be graded as stage I, II or III according to the OMERACT grading principle (Cf appendix 4).

- A VAS recorded during infiltration.
- Verbal score for overall change at 3 months.

The verbal progression scale is a dynamic criterion for assessing disease progression in relation to a given reference. The use of this type of scale is suggested by treatises on the measures to be used in research projects in osteoarthritis, and the scale has proved its effectiveness in a large number of trials. 

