### 4.2.2.2. Ultrasound-guided infiltration technique

Infiltrations will be performed on each site in a standardized manner.

The patient is placed in a supine position with arms extended at the side of the body, hands resting on a hard surface, and the palm of the hand to be infiltrated facing upwards.

The reference section is the longitudinal section of the palmar aspect of the joint. The trapeziometacarpal joint is identified as the hypoechoic zone between the 2 bones.

The joint is approached perpendicularly to the probe: the approach is generally lateral to medial but can be easily performed in the other direction depending on the patient's position and the operator's experience. In this technique, the needle appears as a hyperechoic point with a comettail artefact. The needle is introduced perpendicularly to the probe at an angle of 30° to 45° until the hyperechoic spot appears. A 25 G subcutaneous needle is used, with local anesthesia using Xylocaine for the subcutaneous planes and passage of the capsule.

The criterion for success is that the infiltration is performed without resistance, with distension of the capsule observed on ultrasound.

This technique was chosen because it allows intra-articular verification as shown by Di Sante who administered intra-articular injections of hyaluronic acid using a perpendicular approach to the probe, and in 100% of the patients obtained a bulging appearance of the capsule after injection, indicating the intra-articular localization of the product. 

Similarly, in an anatomical study, Umphrey et al demonstrated the intra-articular localization of the infiltration product by arthrography in 17 cadavers, with 16 (94%) actually having had an intra-articular injection. 

Depending on the randomization arm, either 0.5 ml of CTC and 0.5 ml of 0.9% NaCl; or 0.5 ml of CTC and 0.5 ml of HA will be injected.

During these infiltrations, a sterile drape will be placed vertically on an infusion stand, to ensure patient "blinding".

Therefore, the operator will not be blinded; but this doctor will not be the evaluating doctor, who will be effectively blinded to the product(s) injected.

Each infiltration will be followed, if necessary, by a 48-hour work stoppage in accordance with standard practice.

Each patient will be fitted with a resting orthosis for use at night.

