### Study schedule:

Actions	M-1 (Pre-inclusion visit)	M0 (Inclusion visit)	M1	М3	M6	M12
Checking inclusion/non-inclusion criteria	X					
Signing the informed consent		X				
History	X					
Clinical examination		X	X	X	X	X
Randomization		X				
VAS at rest		X	X	X	X	X
VAS for thumb-index grip (during activity)		X	X	X	X	X
VAS for infiltration		X				
Worst Pain Score		X	X	X	X	X
Cochin scale		X	X	X	X	X
Verbal score for overall change			X	X	X	X
Dynamometer (2x3 measurements)		X	X	X	X	X
B-mode and Doppler ultrasound		X		X		
Concomitant treatments (analgesics, NSAIDs)		X	X	X	X	X
Adverse events		X	X	X	X	X

\* Weekly VAS for the first 3 months will be recorded in the patient's diary. The use of new infiltrations, the number of days off work and any progression to a surgical procedure will be recorded during the 12 months of follow-up.

The time allowed for visits at M1 and M3 (primary endpoint) is  $\pm$ 4 days. The time allowed for the other follow-up visits (M6 and M12) is  $\pm$ 4 week.

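### Injection pain is compared by an unadjusted t test; adjusting for M0 rest pain and center would be a free, possibly small, gain in precision

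*Combined protocol and SAP*

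**What the plan says.** Comparing injection pain between the arms is a stated secondary objective (section 3.2), and section 4.1.2 lists the endpoint as "A VAS recorded during infiltration". Section 9.1 gives its whole analysis in one line: "The VAS of pain at the time of injection will be compared between the two groups using a Student's t test". No covariate, center term or confidence interval is mentioned.

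Section 4.2.2.1 lists what is collected at the inclusion visit, including "a pain VAS (at rest and during activity), the Cochin scale, grip and opposition strength and a pain VAS during the infiltration procedure". The study schedule in section 4.2.2.3 places rest VAS, activity VAS and "VAS for infiltration" all at M0, the last of these at M0 only.

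On the design, section 4.3.1 says "Randomization will be stratified by center" and "It will be carried out in a 1:1 ratio and in blocks". The primary analysis in section 9.1 compares activity VAS at 3 months with a mixed model "taking account of the initial VAS as a fixed effect and the center as a random effect".

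**The concern.** Injection pain is a continuous score on a VAS. Two other pain VAS scores from the same patient, at the same visit, are already in the database, and the plan shows with its primary model that it is willing to adjust for baseline pain and center. If patients with more thumb pain beforehand also report more pain from the needle, an unadjusted comparison leaves that between-patient variation in the error term.

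Two things are at stake. The interval for the treatment difference may be wider than it needs to be. And since the only stratification factor named is center, the arms can differ by chance in baseline pain, part of which would then show in the observed difference in injection pain. Center is also left out, although the randomization is stratified by it and section 4.2.2.1 has only one or two doctors per center giving the injections.

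**Working it through.** **The plan's own figure.** The documents give no SD, target difference, power or correlation for injection pain, so there is no planned figure for this endpoint to reproduce. The only sample-size figure is for the primary endpoint (section 9.2). The difference is 6.4 × (0.35 − 0.25) = 0.64, with SD 1.3, 80% power and 5% alpha, taken as two-sided. The normal formula gives 65 per arm (130 in all). The t-based calculation gives 65.74, so 66 per arm and 132 in all, as stated. Nothing below affects that figure.

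**Inputs for injection pain**
- Patients: 150 in all (section 9.2), allocated 1:1 (section 4.3.1), so 75 per arm, all assumed to be scored.
- SD of injection VAS: not given. Assumed 2.5 cm, with 1.3 and 2.0 cm as alternatives. The 1.3 in section 9.2 is the SD of baseline pain, not of injection pain.
- Correlation r of baseline pain VAS with injection VAS: not given. Range shown: 0 to 0.5.

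**Precision.** The unadjusted standard error is SD × √(2/75) = 2.5 × 0.1633 = 0.408 cm. Adjustment for one covariate multiplies it by √(1 − r²). The half-width of the 95% interval is 1.976 × SE, where 1.976 is the t quantile on 148 degrees of freedom. The detectable difference at 80% power is (1.960 + 0.842) × SE by the normal formula. The last column is the two-sample t power for an illustrative difference of 1.0 cm, with SD replaced by SD × √(1 − r²).

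| r | √(1 − r²) | SE (cm) | CI half-width (cm) | Detectable difference (cm) | Power for 1.0 cm |
|---|---|---|---|---|---|
| 0 | 1.000 | 0.408 | 0.81 | 1.14 | 68% |
| 0.1 | 0.995 | 0.406 | 0.80 | 1.14 | 69% |
| 0.2 | 0.980 | 0.400 | 0.79 | 1.12 | 70% |
| 0.3 | 0.954 | 0.389 | 0.77 | 1.09 | 72% |
| 0.5 | 0.866 | 0.354 | 0.70 | 0.99 | 80% |

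The relative gain does not depend on the SD. The interval narrows by 0.5%, 2%, 4.6% and 13.4% at r = 0.1, 0.2, 0.3 and 0.5. In patients per arm, r = 0.3 is worth 75/(1 − 0.09) = 82 and r = 0.5 is worth 75/(1 − 0.25) = 100. With SD 2.0 the half-width goes from 1.976 × 0.327 = 0.65 cm to 0.56 cm at r = 0.5. With SD 1.3 it goes from 1.976 × 0.212 = 0.42 cm to 0.36 cm.

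**Chance imbalance.** The part of a baseline imbalance that reaches the unadjusted difference is slope × imbalance, with slope = r × SD(injection)/SD(baseline). For an imbalance of 1.96 standard errors, which is 1.96 × 1.3 × 0.1633 = 0.42 points of activity VAS, the baseline SD cancels and the shift is r × SD(injection) × 1.96 × 0.1633.
- SD 2.5: 0.08, 0.16, 0.24 and 0.40 cm at r = 0.1, 0.2, 0.3 and 0.5.
- SD 1.3: 0.04, 0.08, 0.12 and 0.21 cm at the same values.

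**Validity.** In 20,000 simulated trials under no treatment effect, 75 per arm, at each of r = 0, 0.3 and 0.5, the t test rejected in 4.8%, 5.0% and 4.7% and showed no bias. Adjustment lowered the SD of the estimate, in SD units, from 0.163 to 0.156 at r = 0.3 and from 0.162 to 0.141 at r = 0.5. At r = 0 it went from 0.1626 to 0.1632, so adjusting for a useless covariate costs almost nothing. The simulation did not include center.

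**The case against.** The strongest case against is that nothing here is wrong. A two-group t test is a standard analysis of a single score measured once after randomization. Its standard error already allows for chance imbalance in every covariate, measured or not. That stands. A reader might infer that a baseline imbalance passes whole into the result, or that the t test mistakes it for a treatment effect. Neither holds: only slope × imbalance passes through, the test is unbiased over randomization, and it keeps its 5% level.

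It also stands that the gain is not established. The documents supply no correlation, and section 4.2.2.2 gives a reason to expect a low one: the injection is done "with local anesthesia using Xylocaine for the subcutaneous planes and passage of the capsule". Procedural pain under local anesthetic is a different quantity from usual thumb pain. At r of 0.2 or less the interval narrows by at most 2%.

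Nor is the omission inconsistent with the primary model. That model adjusts activity VAS for its own baseline value, whereas injection pain has none. Finally, the documents do not say that rest and activity VAS are scored before the needle goes in. Their role as baseline makes it likely, but it is not written.

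What the objection does not remove is that a candidate covariate is already collected, that center is a stratification factor left out of the analysis, and that prespecified adjustment costs next to nothing if r turns out to be zero.

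**Conclusion.** The planned analysis is valid, and it may be less efficient than the collected data allow. With SD 2.5 cm and 75 per arm, adjusting for one baseline pain score takes the 95% interval half-width from 0.81 cm to somewhere between 0.81 cm (r = 0) and 0.70 cm (r = 0.5). Both the SD and r are assumptions. A firm statement that precision is lost would go beyond the documents, and so would any claim of bias or inflated error. The contribution of center cannot be sized from the documents.

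This is an optional improvement to one secondary endpoint. The sample size and the primary conclusion are unaffected.

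**What to change.** In section 9.1, replace the t test for injection pain by a linear model with treatment group, M0 rest-pain VAS and center, and report the adjusted mean difference with its 95% confidence interval.

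State in the same place, and in section 4.2.2.1, that the rest-pain VAS is scored before the infiltration. A score taken afterwards could itself be affected by the product injected and should not be adjusted for.

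Name the covariate now, so that there is no later choice between rest and activity VAS or between adjusted and unadjusted results. Rest pain is a reasonable choice: the patient lies still for the injection, and activity VAS is cut off at 4 by the population description in section 2.6, which narrows its range.

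The cost is a few lines of wording and no new data. With three centers as fixed effects, the model uses one degree of freedom for rest pain and two for center, so 148 − 3 = 145 remain.
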